7.4 Serious Adverse Events (SAE)	47
7.5 Serious and Unexpected Suspected Adverse Reaction (SUSAR)	48
7.6 SAE Report Procedure	48
7.6.1 Expedited Reporting of SAEs	48
7.6.2 IRB Notification	48
7.6.3 Record Retention	49

8. Statistic Methods	50
8.1 Sample Size Determination	50
8.2 Statistical Method	50
8.3 Analysis of Efficacy and Safety	51
8.4 Premature Termination and Handling of Missing Data	51
9. Quality Control and Quality Assurance	52
9.1 Study Monitoring	52
9.2 Sponsor Auditing	52
9.3 Inspected by Regulatory Authorities	52
10. Ethical Considerations	53
10.1 Confidential	53
10.2 Protocol Amendment	53
10.3 Informed Consent	53
10.4 Institutional Review Board (IRB)	54
11. Data Handling and Record Keeping	55
11.1 Data Handling and Collection	55
11.1.1 Study Specific Binders	55
11.1.2 Responsibilities of Investigators	55
11.1.3 Responsibilities of Clinical Monitor	56
11.2 Records Retention	56
11.2.1 Source Document Retention	56
11.2.2 CRF Retention	57
11.2.3 Record Maintenance	57
11.3 Investigator Study File Management	57
12. Publication Plan	59
13. References	60

PROTOCOL SYNOPSIS

Name of sponsor	BioLite, Inc. / American BriVision Corporation
Name of finished product	PDC-1421 Capsule
Name of active ingredient	PDC-1421
Protocol title	A Phase II Tolerability and Efficacy Study of PDC-1421 Treatment in Adult Patients with Attention-Deficit Hyperactivity Disorder (ADHD), Part II
Clinical trial phase	Phase II
Study site	Multiple sites
Study period	2 years
Study population	Patients with ADHD according to the Diagnosis and Statistical Manual of Mental Disorders, 5th Edition
Primary study objective	To determine the efficacy profile of PDC-1421 Capsule in ADHD with ADHD Rating Scale-IV (ADHD-RS-IV).
Secondary study objective	To determine the efficacy and safety profile of PDC-1421 Capsule in ADHD with other rating scales.
Study design	Randomized, double-blind, placebo-controlled, parallel groups
Sample size	Maximum 99 subjects
Test product	PDC-1421 Capsule
Dose and regimen	1 and 2 capsules thrice daily, p.o., after meal
Duration of treatment	56 days
Study intervention	
The screening phase is intended for diagnosing and assessing the patient for possible inclusion in the study and for providing an adequate washout period.
 
Part II is a randomized, double-blind, placebo-controlled, parallel-group study. At first stage, a number of 69 subjects will be randomly assigned on a 1:1:1 basis to one of the three arms (1 PDC-1421 Capsule plus 1 placebo TID, 2 PDC-1421 Capsules TID, 2 placebo TID) for 8 weeks and evaluated the safety and efficacy every two weeks during the treatment period. An interim analysis will be conducted to evaluate the efficacy of PDC-1421 and to decide whether

	it is necessary enter the second stage of Part II study in which 30 subjects will be randomly assigned on a 1:1:1 basis to one of the three treatment arms and receive the same treatment.
Primary endpoint	
 Improvement of 40% or greater in ADHD Rating Scale-Investigator Rated (ADHD-RS-IV) from baseline up to 8 weeks treatment
Secondary endpoints	
 Symptom remission in ADHD Rating Scale-Investigator Rated (ADHD-RS-IV total score ≤ 18) up to 8 weeks treatment. Change from baseline in the ADHD Rating Scale-Investigator Rated (ADHD-RS-IV), Conners' Adult Attention-Deficit/Hyperactivity Disorder Rating Scale-Self Report: Short Version (CAARS-S:S) and Empirical-Sluggish Cognitive Tempo (E-SCT) score up to 8 weeks treatment. Clinical Global Impression - improvement (CGI-I) score of 2 or lower up to 8 weeks treatment.
Safety Evaluation	
A. Change from baseline in:
 
 vital sign physical examination electrocardiogram (ECG) laboratory tests (hematology and biochemistry) 
B. Incidence of AE/SAE
 
C. Suicidal ideation and behavior by Columbia-Suicide Severity Rating Scale (C-SSRS)

Statistical method	
Simple descriptive statistics with 95% confidence interval will be performed with data collected in this study wherever applicable. The safety and efficacy data will be analyzed using the non-parametric method wherever appropriate.
 
The primary endpoint will be analyzed by chi-square test, while the secondary endpoints will be analyzed using the ANOVA or Kruskal-Wallis non-parametric ANOVA test for continuous endpoints and chi-square test for binary endpoints.

LIST OF ABBREVIATIONS/DEFINITIONS

- ADHD
Attention-Deficit/Hyperactivity Disorder
- ADHD-RS-IV
Attention-Deficit/Hyperactivity Disorder Rating Scale-IV
- AE
Adverse Events, whether or not considered related to the investigational drug, must be recorded in CRF.
- CAARS-S:S
Conners' Adult Attention-Deficit/Hyperactivity Disorder Rating Scale-Self Report: Short Version
- CGI-I
Clinical Global Impression- Improvement
- CGI-S
Clinical Global Impression- Severity
- CHO
Chinese Hamster Ovary
- Clinical monitor
The designated CRA monitoring this study for the sponsor
- CRA
Clinical Research Associate
- CRC
Clinical Research Coordinator
- CRF
Case Report Form
- CRO
Contract Research Organization
- C-SSRS
Columbia-Suicide Severity Rating Scale
- DLT
Dose limiting toxicities
- DSM-5
The Diagnostic and Statistical Manual of Mental Disorders, Fifth Edition

- ECG
The Electrocardiogram (ECG) is a graphical recording of the cardiac cycle produced by an electrocardiograph.
- HDL
High-Density Lipoprotein
- HED
Human Equivalent Dose
- HPLC
High Performance Liquid Chromatography
- ICF
Informed Consent Form
- ICH-GCP
International Conference of Harmonization-Good Clinical Practice
- IEC
Independent Ethics Committee
- IRB
Institutional Review Board
- LDH
Lactate Dehydrogenase
- E-SCT
Empirical-Sluggish Cognitive Tempo
- LDL
Lower-Density Lipoprotein
- NET
Norepinephrine Transporter
- NLT
Not Less Than
- NMT
Not More Than
- NOAEL
No Observable Adverse Effect Level
- NRI
Norepinephrine Reuptake Inhibitor
- PITDC

Medical and Pharmaceutical Industry Technology and Development Center

- SAEs

Serious Adverse Event(s), whether or not considered as related to the investigational drug must be recorded and reported.

The serious adverse event is defined as following:

Death

Life-threatening condition

Inpatient hospitalization or prolongation of existing hospitalization

Persistent or significant disability/incapacity

Congenital anomaly/birth defect

Required intervention to prevent permanent impairment/damage

- Severity Rating of AE

Grade 1 Mild; asymptomatic or mild symptoms; clinical or diagnostic observations only; intervention not indicated.

Grade 2 Moderate; minimal, local or noninvasive intervention indicated; limiting age-appropriate instrumental activities of daily living (ADL)*.

Grade 3 Severe or medically significant but not immediately life-threatening; hospitalization or prolongation of hospitalization indicated; disabling; limiting self care ADL†.

Grade 4 Life-threatening consequences; urgent intervention indicated.

Grade 5 Death related to AE.

*Instrumental ADL refer to preparing meals, shopping for groceries or clothes, using the telephone, managing money, etc.

†Self care ADL refer to bathing, dressing and undressing, feeding self, using the toilet, taking medications, and not bedridden.

- SHR

Spontaneous hypertensive rat

- SOP

Standard Operation Procedure

- Study Cohort

The Study Cohort is defined as a group or cohort of subjects who are assigned to take the same dose level of the study drug.

- TID

Three times a day

- WKY rat

Protocol

Wistar-Kyoto rat

- TLC

Thin Layer Chromatography

1. Background Information

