4.1 Inclusion Criteria

1. Aged 18-70 years
2. Female subjects of child-bearing potential must test negative to pregnancy and use appropriate birth control method from the beginning of study to the 15 days later after ending of study
3. Subjects must be able to understand and willing to sign informed consent
4. Able to discontinue the use of any psychotropic medications for the treatment of ADHD symptoms at screening
5. Meet strict operational criteria for adult ADHD according to the Diagnostic and Statistical Manual of Mental Disorders, 5th Edition (DSM-5)
6. A total score of 28 or higher of ADHD Rating Scale-Investigator Rated (ADHD-RS-IV) at screening
7. Have a moderate or severe symptom of ADHD with score of 4 or higher in Clinical Global Impression- Severity (CGI-S) at screening

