6.2 Methods and Timing for Assessing, Recording, and

Analyzing of Efficacy Parameters.

The data obtained from eligible subjects before study drug administration in Visit 2 or Visit 1 (if no data at Visit 2) are set as baseline. After the beginning of treatment, the collection of data of efficacy parameters are performed at planned treatment schedule as [section 5.2](#). CRC shall record these data in CRF in detail after each visit during the treatment period. In part II, data comparison between group of 1 capsule TID, 2 capsules TID of PDC-1421 Capsule and 2 capsules TID of placebo will be conducted in final report of this study to evaluate which group(s) of PDC-1421 Capsule are efficient. The rating scales are as follows:

- **ADHD-RS-IV**

The ADHD-RS-IV with Adult Prompts is an 18-item scale base on the DSM-IV-TR' criteria for ADHD that provides a rating of the severity of symptoms¹⁵. The adult prompts serve a guide to explore more fully the extent and severity of ADHD symptoms and create a framework to ascertain impairment. The odd-numbered 9 items assess inattentive symptoms and the even-numbered 9 items assess hyperactive-impulsive symptoms. Scoring is based on a 4-point, yielding a possible total score of 0 – 54. Likert-type severity scale: 0 = Never or Rarely, 1 = Sometimes, 2 = Often, 3 = Very Often. Clinicians should score the highest score that is generated for the

prompts for each item.

For inattention (IA) subscale raw score: Add the odd-numbered 9 items

For hyperactivity-impulsivity (HI) subscale raw score: Add the even-numbered 9 items

To obtain the total raw score: Add the IA and HI subscale raw scores.

- **Clinical Global Impression¹⁶**

At the baseline visit, clinicians completed the CGI-S and were asked to evaluate the severity of subjects' illness with respect to ADHD symptoms based on the clinician's experience with this particular population. Possible scores ranged from 1 (normal, not at all ill) to 7 (among the most extremely ill). At all subsequent study visits, clinicians used the CGI-I to rate the subjects' total improvement based on comparison with their baseline assessment from 1 (very much improved) to 7 (very much worse).

- **CAARS-S:S**

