8.2 Statistical Method

Simple descriptive statistics with 95% confidence interval will be performed with data collected in this study wherever applicable. All data shall be tabulated and presented in the study report. The safety and efficacy data will be analyzed using the non-parametric method wherever appropriate.

The baseline demographic characteristics within each cohort will be compared using chi-square test or exact test for categorical variables and ANOVA (analysis of variance) or Kruskal-Wallis non-parametric ANOVA test for continuous variables. The primary endpoint will be analyzed by chi-square test, while the secondary endpoints will be analyzed using the ANOVA or Kruskal-Wallis non-parametric ANOVA test for continuous endpoints and chi-square test for binary endpoints. Since this is only a small proof-of-concept study, no multiple comparisons will be made to adjust the p-values for all pairwise comparisons.

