5.4 Changes in the Conduct of the Study or Planned Analyses

All the statistical analysis will follow protocolized statistical contents. However, due to the interim report results do not meet the requirement of protocol and the study was terminated, the chi-Square test and Wilcoxon signed-rank test between arms will not be performed.

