6.6.2 Secondary Efficacy Endpoints

- **ADHD-RS-IV**

The scores of ADHD-RS-IV will be assessed by the descriptive statistics.

- **CGI**

The scores of 2 or lower of CGI will be summarized by way of frequency and percentage.

At the screen and baseline visit, clinicians completed the CGI-S and were asked to evaluate the severity of subjects' illness with respect to ADHD symptoms based on the clinician's experience with this particular population. Possible scores ranged from 1 (normal, not ill at all) to 7 (among the most extremely ill subjects). At all subsequent study visits, clinicians used the CGI-I to rate the subjects' total improvement based on comparison with their baseline assessment from 1 (very much improved) to 7 (very much worse).

- **CAARS-S:S**

The T-scores of CAARS-S:S (Conners et al. 1999) will be assessed for each visit change from baseline by the descriptive statistics

Conners' Adult Attention-Deficit/Hyperactivity Disorder Rating Scale-Self Report: Short Version (Conners et al., 1998; CAARS-S:S) consists of 26 items rated from 0 'not at all, never' to 3 'very much, very frequently.' Four subscales each composed of 5 items (A: Inattention/Memory Problems; B:

Hyperactivity/Restlessness; C: Impulsivity/Emotional Lability; and D: Problems with Self-Concept) as well as a 12-item ADHD index can be computed. The raw scores were converted into standard T-scores by Microsoft Excel program which designed according to the Profile form of CAARS QuikScore forms. A T-score is a standard score with a mean of 50 and a standard deviation of 10 in all samples and across all scales. As a general guide, T-scores can be interpreted using the guidelines provided in the table below. The CAARS-S:S was self-assessed by the subjects from Visit 1 to Visit 7.

Interpretive Guidelines for T-Scores and Percentiles

T-Score Range	Percentile Range	Guideline
Above 70	98+	Very much above average
66 to 70	94 - 98	Much above average
61 to 65	86 - 94	Above average
56 to 60	74 - 85	Slightly above average
45 to 55	27 - 73	Average
40 to 44	16 - 26	Slightly below average
35 to 39	6 - 15	Below average
30 to 34	2 - 5	Much below average
Below 30	< 2	Very much below average

Reference: CAARS Adult ADHD Rating Scales Technical Manual

• E-SCT

The scores of E-SCT will be assessed for each visit change from baseline by the descriptive statistics

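### Remission (ADHD-RS-IV total of 18 or lower) depends materially on the entry score, but neither the protocol's chi-square nor the SAP's descriptive summary adjusts for it; the cost is modest precision and exposure to chance imbalance, not validity

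*Protocol*

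**What the plan says.** **Endpoint.** The protocol synopsis and section 3.3 list as a secondary endpoint "Symptom remission in ADHD Rating Scale-Investigator Rated (ADHD-RS-IV total score ≤ 18) up to 8 weeks treatment". SAP 5.3.2 keeps it.

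**Entry range.** Protocol 4.1 requires "A total score of 28 or higher of ADHD Rating Scale-Investigator Rated (ADHD-RS-IV) at screening". Protocol 6.2 describes the scale as "yielding a possible total score of 0 – 54".

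**Test in the protocol.** Section 8.2 reads "The primary endpoint will be analyzed by chi-square test, while the secondary endpoints will be analyzed using the ANOVA" or Kruskal-Wallis for continuous endpoints, and "chi-square test for binary endpoints". The synopsis likewise assigns the secondary endpoints ANOVA or "Kruskal-Wallis non-parametric ANOVA test for continuous endpoints and chi-square test for binary endpoints". Neither document names a covariate or an adjusted model, and Protocol 3.4 states no stratification by baseline score.

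**Baseline.** Protocol Table 15 schedules the ADHD-RS-IV at Visits 1 and 2. Protocol 6.2 and SAP 6.4 set baseline as the pre-dose Visit 2 value, or Visit 1 if Visit 2 is missing. SAP 6.3 looks at baseline characteristics across arms for comparability but does not carry them into any efficacy analysis.

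**Final SAP.** Section 5.4 records that the study was terminated after the interim analysis and that "the chi-Square test and Wilcoxon signed-rank test between arms will not be performed". Section 6.6.2 says "The scores of ADHD-RS-IV will be assessed by the descriptive statistics" and gives remission no analysis of its own. Section 6.2 gives categorical variables a frequency and percentage only.

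**The concern.** The change scores and the 40% responder endpoint both contain the subject's own baseline; remission does not. Two subjects with the same percentage improvement can be classified differently only because one entered more severe. If one arm starts milder by chance, it will tend to show more remission without any drug effect, and a raw table gives the reader no way to separate the two. With 23 subjects per arm at stage I, or 33 if stage II had run, such imbalances are ordinary. The score needed to correct for them is already collected in the schedule, so leaving it out also discards some precision at no saving.

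**Working it through.** **1. The plan's own figures.** The documents state no size, power or expected rate for remission. The stated design (alpha 0.15, power 80%, 23 + 10 per arm, continue if the responder difference is at least 0, reject the drug if the cumulative difference is below 4) concerns the primary endpoint. For one dose against placebo, an exact two-binomial calculation gives alpha 0.139 at 20% v 20% and power 0.801 at 20% v 40%. The design reproduces, but it says nothing about remission.

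**2. Fall needed to reach 18** (from the documents alone): (entry − 18) / entry.

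| Entry score | Points | Fall |
|---|---|---|
| 28 | 10 | 35.7% |
| 30 | 12 | 40.0% |
| 36 | 18 | 50.0% |
| 45 | 27 | 60.0% |
| 54 | 36 | 66.7% |

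At an entry score of 30, remission coincides with the primary 40% criterion. Below 30 it is easier than response; above 30 it is harder. The floor of 28 applies at screening and no floor is stated for Visit 2, so the baseline range may be wider than this.

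**3. Shift from a chance imbalance.** Assumptions not in the documents: 20% remission in both arms, roughly bivariate-normal baseline and Week 8 totals, correlation r = 0.30, 0.45 or 0.60.
- One standard error of the baseline mean difference at 23 per arm is sqrt(2/23) = 0.295 baseline SDs. With an assumed SD of 5.2 to 5.6 points this is 1.5 to 1.7 points.
- One baseline SD moves remission by about r × φ(−0.842) = r × 0.280, where −0.842 is the normal 20% point.
- Shift = r × 0.280 × 0.295 = r × 8.26 percentage points, which is 2.5 / 3.7 / 5.0 points.
- Sampling standard error of the difference = sqrt(2 × 0.2 × 0.8 / 23) = 11.8 points. The shift is therefore 2.5/11.8 = 0.21 to 5.0/11.8 = 0.42 standard errors.

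At 33 per arm the factor is 0.280 × sqrt(2/33) = 6.9 points × r, so the shift is 2.1 to 4.1 points against a standard error of 9.8.

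**4. Does adjustment remove it?** In simulated null trials where placebo started more than one standard error worse (r = 0.3 to 0.7, 23 or 33 per arm; baseline mean 37, Week 8 SD 10), the raw difference averaged +3.6 to +7.4 points. The baseline-standardised difference averaged −0.5 to +0.8.

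**5. Type I error.** Over all null trials in the same simulation, the unadjusted chi-square at two-sided 0.05 rejected 4.7% to 5.5%.

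**6. Precision and power** (assumed 20% v 40% remission, two-sided 0.05, logistic score test with continuous baseline, r = 0.30 / 0.45 / 0.60).
- 33 per arm: variance of the difference falls by about 4% / 8% / 18%. Power rises from about 44% to 45% / 47% / 52%. A second simulation gave about 43–45% rising to 45% / 49% / 50%. Null rejection was about 5%.
- 23 per arm: power rises from about 31–32% to 34% / 35% / 39%. Null rejection was 5.4% to 6.4%, so part of this gain is small-sample anticonservatism.

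**The case against.** The case against making much of this is strong, and most of it stands.

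- **The test is no longer planned.** A reader of the protocol alone might infer that remission will be compared by chi-square. SAP 5.4 withdraws that test. What survives is narrower: the protocol text as written, and raw remission rates in any SAP table.
- **No validity error.** One might infer that imbalance produces false positives. Under randomisation, chance imbalance is already inside the test's error rate, and the simulated null rejection shows no inflation. The shifts in step 4 come from selecting trials that were imbalanced; averaged over all trials the comparison is unbiased.
- **Entry score does not fix the outcome.** The spread from 35.7% to 66.7% invites the reading that remission is largely decided at entry, or that baseline is its strongest predictor. The documents give no correlation or predictor ranking. At the assumed 0.3 to 0.6, baseline explains only 9% to 36% of the Week 8 variance (r squared).
- **Low consequence.** The go/no-go rule uses responder counts on the primary endpoint only, and the protocol describes the study as a small proof of concept.
- **Few events.** At 20% remission, 23 per arm gives about 5 remitters (0.2 × 23 = 4.6). A rule that changes method when an arm has fewer than 5 would be triggered with probability about 0.50 in one arm, hence 1 − 0.50² = 0.75 in at least one of two. That argues against a data-driven switch, not against adjustment.

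The objection does not remove the two residual costs: lost precision, and a raw difference that carries any baseline imbalance with it. Comparing baselines between arms can reveal an imbalance but does not correct the remission result.

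**Conclusion.** The point holds as a minor analysis-choice weakness. That remission lacks a baseline term, and that the required fall nearly doubles across the permitted entry range, follows from the documents' own figures. The size does not: it rests on assumed correlations of 0.3 to 0.6 and assumed remission rates of 20% and 40%. On those, a one-standard-error imbalance at 23 per arm moves the remission difference by roughly 2 to 5 percentage points, well under its sampling standard error of about 12, and adjustment adds roughly 1 to 8 points of power. At the low end of the correlation range the gain is slight. The documents do not support a claim of inflated type I error, nor a claim that the current SAP tests remission by chi-square.

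**What to change.** **Protocol 8.2 (and synopsis), for this or any reuse of the design.** Name one pre-specified comparison of Visit 6 remission for each dose against placebo: a logistic score test with treatment and the continuous baseline ADHD-RS-IV total, reporting the baseline-standardised risk difference with 95% CI. Do not let the number of remitters change the method. A Mantel-Haenszel difference over two baseline strata, split at the pooled median, is a simpler alternative with less gain.

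**SAP 6.6.2.** Give remission its own entry. Report the count and percentage by arm together with that baseline-adjusted difference and 95% CI, labelled descriptive and supportive. Do not reinstate a between-arm test.

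**Cost.** One sentence in each document and one extra model. No new data, visits or subjects. The drawback is slight small-sample imprecision at 23 per arm, which the descriptive label covers.

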1.1 Description of PDC-1421 Capsule

PDC-1421 Capsule is a botanical investigational new drug containing the extract of Radix Polygalae (*Polygala tenuifolia* Willd.) as active ingredient. Radix Polygalae is a traditional herb commonly prescribed in China to induce sedation, benefit the mentality and to promote expectoration. It has also been used for insomnia, anxiety, and heart palpitations¹.

1.1.1 Preparation

Raw materials originated from *P. tenuifolia* were obtained from Shanxi, China. After having been cleaned, and residual stems removed, the root was sun-dried and become the botanical raw material for producing the study drug (PDC-1421 capsule). Raw materials shall comply with physical/chemical specifications, and fingerprint determination via HPLC and TLC shall show desired contents. The materials shall comply criteria for heavy metal, pesticide residues and aflatoxins to avoid contaminations. Acceptable raw materials were water extracted, partially purified by column chromatography, concentrated, and spray-dried to become the drug substance PDC-1421, a yellowish powder. The yield rate from raw materials to PDC-1421 is about 1.4%. Formulation and encapsulation of drug substance PDC-1421 produced the final product of PDC-1421 Capsule. Specifications of PDC-1421 Capsule are tabulated in [Table 1](#).

Table 1. Specifications of PDC-1421 Capsule

Test Items	Specifications
Physical Appearance	Yellowish Granules in brownish capsule.
Loss on Drying	NMT 6%
Water Extractives	NLT 80%
Dilute-Alcohol Extractives	NLT 70%
Total Ash	NMT 5%
Acid-Insoluble Ash	NMT 4%
Alcohol Extractives	NLT 38%
TLC	1. One grayish blue band has same R_f value as reference standard (3',6-disinapoylsucrose); 2. One watchet blue band has same R_f value as reference standard (Glomeratose A).
HPLC of markers	1. $10.0 \text{ mg/g} \leq \text{Glomeratose A} \leq 30.0 \text{ mg/g}$. 2. $38 \text{ mg/g} \leq 3',6\text{-Disinapoylsucrose} \leq 95 \text{ mg/g}$.
UV Spectrum	λ_{max} : 230 – 240 nm; 315 – 325 nm
IR Spectrum (cm^{-1}, %T)	Peak at: 3380 ± 100 Broad, 2938 ± 20 Sharp, 1605 ± 10 Sharp, 1455 ± 10 Sharp, 833 ± 10 Sharp.
pH	Dissolved in distill deionized water at a concentration of 0.1 g/ml, $3.8 \leq \text{pH} \leq 5.8$.
Uniformity	90-110%
Weight Variation	90-110%
Heavy Metal	Cu < 20 ppm, As < 1 ppm, Pb < 5 ppm, Cd < 0.2 ppm, Hg < 0.1 ppm
Microbial Purity	Total aerobic plate count: NMT 10^3 CFU/g Mold and yeast count: NMT 100 CFU/g Escherichia coli : Undetectable Staphylococcus aureus : Undetectable Salmonella : Undetectable

NMT: not more than; NLT: not less than

PDC-1421 used in phase I clinical trial was manufactured at the Medical and Pharmaceutical Industry Technology and Development Center (PITDC) in New Taipei City, Taiwan. In order to scale up the production and in compliant with GMP (Good Manufacturing Procedures), the producer has been changed to the Herbal Medicine GMP Plant of the Industrial Technology Research Institute (ITRI) in Hsinchu County, Taiwan. Products produced at ITRI Plant have been tested and meet defined specifications prior to be used in this study.

